### 8.3 SERIOUS ADVERSE EVENTS AND DEATHS

- Treatment-Emergent Serious adverse events (SAEs) will be summarized by system organ class and preferred term. The number and percentage of the subjects who experienced at least one SAE will be included.
- SAE data will be evaluated for each treatment group (Zimura 4 mg, 2 mg, and 1 mg).
- Tabular summaries of the following SAEs will be provided:
  - All SAEs regardless of the relationship to study treatment
  - SAEs related to study treatment
  - SAEs related to injection procedure
  - Ocular SAEs (study eye) regardless of the relationship to study treatment
  - Ocular SAEs (study eye) related to study treatment
  - Ocular SAEs (study eye) related to injection procedure
- In addition, separate listings will be created for deaths and all SAEs. List for SAEs will include the subject identifier, age, sex, verbatim term, preferred term, eye (N/A/OD/OS/OU), serious (yes/no), date of onset, relative study day of onset, onset before

injection, after first injection or after second injection, duration of the event (or continuing), severity (mild/moderate/severe), causality (relationship to study medication/injection procedure), action taken (study drug permanently discontinued: yes/no), treatment (yes/no), and outcome (resolved/unresolved/fatal).

### 8.4 VITAL SIGNS

Descriptive statistics at each time point up through and including the month 12 visit will be used to display the changes from Baseline for pulse and blood pressure (systolic and diastolic). Mean change of pulse and blood pressure (systolic and diastolic) from Baseline to the last measurement will be provided.

### 8.5 **OPHTHALMIC VARIABLES**

**Ophthalmic Examination.** The following ophthalmic examination variables will be analysed by shift table from Baseline to the pre-injection examination on Month 12 or last visit available whichever comes later (normal/abnormal, unless otherwise specified below).:

- Examination of the motility
- Inspection of the lids/lacrimal/lashes
- Examination of the conjunctiva/sclera
- Inspection of the cornea
- Examination of the iris
- Examination of the pupils
- Inspection of the lens status (aphakic, pseudo-phakic, phakic; if phakic, nuclear/PSC/cortical 0, 1, 2, 3, 4), including a listing of subjects with a change in lens status for study eye and (separately) for fellow eye
- Examination of the posterior vitreous detachment
- Inspection of the optic nerve
- Inspection of the macula
- Examination of the retinal vessels

The following ophthalmic examination variables will be analysed by shift table from Baseline through Month 12 or last visit available whichever comes later, on a monthly basis (normal/abnormal, unless otherwise specified below), and from pre-injection to post-injection at each monthly injection

- Examination of the anterior chamber activity: Cells (0, trace, 1+, 2+, 3+, 4+)
- Inspection of the vitreous haze (0, 1+, 2+, 3+, 4+)
- Examination of the vitreous haemorrhage

• Examination of peripheral retina

**Intraocular Pressure.** IOP will be summarized by visit, including all pre-injection, "IOP after first injection" and "IOP after second injection" measurements. An additional tabular summary of the percentage of subjects in categories of IOP will be presented by treatment group, visit, and injection time (pre-injection, IOP after first injection, IOP after second injection).

"IOP after injection" is defined as the IOP measurement that is closest in time to the protocolspecified post-injection timepoint (but at least 25 minutes post-injection). If there are two closest measurements equidistant to this timepoint, then the measurement after the protocol-specified timepoint will be used.

Mean IOP over time of all scheduled measurements (pre-injection, IOP after first injection, and IOP after second injection) will be plotted.

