### 9.1.2 Treatment Regimen and Duration

Subjects randomized to active drug or Sham will receive monthly injections of Zimura™ or Sham for 18 months. Monthly doses should be administered at least 21 days apart.

- Part 1 Subjects:
  - Subjects randomized to the Zimura™ 1 mg/eye treatment arm will receive Zimura™ 1 mg/eye (50 µL) intravitreal injection.
  - Subjects randomized to the Zimura 2 mg/eye treatment arm will receive Zimura™ 2 mg/eye (100 µL) intravitreal injection.

- Subjects randomized to the Sham treatment arm will receive Sham injections.
- Commencing with Amendment C, no new subjects will be enrolled in Part 1 of this trial. Subjects in Part 1 who have received greater than or equal to 18 months of Study Drug treatment will be discontinued from the study after Amendment C.
- Part 2 Subjects:
  - Subjects randomized to the Zimura™ 2 mg/eye treatment arm will receive a Zimura™ 2mg/eye injection (100 µL) and a Sham injection
  - Subjects randomized to the Zimura™ 4 mg/eye treatment arm will receive two injections of Zimura™ 2 mg/eye. The injection volume for subjects randomized to this arm will be of (100 µL) per injection.
  - Subject's randomized to the Sham treatment arm will receive 2 Sham injections.

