### **10.2.3.27 Month 13 ( $\pm 7$ days)**

#### **Pre-Injection**

- Protocol refraction and visual acuity (4 meters) using ETDRS chart (SE)
- Low Luminance ETDRS Visual Acuity (SE)
- Tonometry and Ophthalmologic examination (SE)
- Randomized Treatment: Zimura™/Sham

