### 11.3 Determination of Sample Size and Statistical Rationale

The sample size determination for this study is based on [REDACTED] screening methodology presented in Fleming and Richardson (2004). The power calculations are based on the recently released results from a clinical trial of a complement inhibitor, including the estimated precision of the estimated effects on rate of GA growth over 12 months, and including the plausible effect size for Zimura™.

A total of approximately 277 subjects will be enrolled. When follow-up is complete for the primary analysis based on 12-month follow-up, the data base will be locked. Information post-12 months will remain fully confidential until completion of 18-month follow-up. By pre-specification, a hierarchical analysis will be performed where the treatment effect on the rate of GA growth over 18 months will be statistically assessed if statistical significance is achieved on the rate of GA growth over 12 months.

[REDACTED] the primary analyses will be based on comparisons of Zimura™ 2 mg vs the Sham control, and Zimura™ 4 mg vs Sham control. For the comparison of Zimura™ 2 mg vs Sham control, the 26 subjects randomized to Zimura™ 2 mg and 26 subjects randomized to Sham control from Part 1 will be combined with the 40 subjects randomized to Zimura™ 2 mg and 80 subjects randomized to Sham control from Part 2, where the analysis will be stratified by Part 1 vs Part 2. The comparison of Zimura™ 4 mg vs Sham control will be based on the 80 subjects randomized to each of these two arms in Part 2.

The primary analysis [REDACTED] for each of the two pairwise comparisons of an active dose of Zimura™ vs the Sham control is formally based on a three-category decision guideline. To be specific, the decision guideline for this trial is based on whether the estimated reduction in rate of GA growth over 12 months for a dose of Zimura™ versus Sham control is less than 14%, is from 14% up to 24.5%, or is at least 24.5%.

Note that these categories should not be interpreted as providing strict decision rules but rather as guidelines that will be factored into a broader scientific assessment of the benefit to risk profile of the Zimura™ dose regimen. This broader assessment will include consideration of safety, of supportive efficacy endpoints, and of relevant information external to this trial. Specifically, the decision guidelines for this trial are:

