### **1 INTRODUCTION**

This Statistical Analysis Plan describes the statistical methodology and data handling for the clinical trial with Protocol Number: OPH2003 and Version Date: 28 March 2018.

The trial consists of a total treatment period of 18 months. This SAP covers all analyses to be performed on the 1 year data. By pre-specification, a screening analysis will be performed to assess whether the effect of Zimura on the rate of Geographic Atrophy (GA) growth is plausibly more efficacious (or reliably more efficacious) than that of the sham control on the rate of GA growth over 12 months. Details of an analysis at 18 months, if applicable, will be specified in a separate SAP.

The ICH guideline E3 "Structure and Content of Clinical Study Reports" is used as a guide to the writing of the plan.

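### The ophthalmic shift tables in SAP 8.5 end at the later of Month 12 and the last visit, so read literally the 12-month analysis uses post-Month-12 examinations

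*SAP*

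**What the plan says.** SAP 8.5 has two groups of ophthalmic shift tables.

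- The first (motility, lids, conjunctiva, cornea, iris, pupils, lens status, posterior vitreous detachment, optic nerve, macula, retinal vessels) has one endpoint per subject: "shift table from Baseline to the pre-injection examination on Month 12 or last visit available whichever comes later".
- The second (anterior chamber cells, vitreous haze, vitreous haemorrhage, peripheral retina) is a series: "shift table from Baseline through Month 12 or last visit available whichever comes later, on a monthly basis". It adds shifts from pre- to post-injection at each monthly injection.

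Two statements govern the time frame. SAP 1 says: "This SAP covers all analyses to be performed on the 1 year data"; any 18-month analysis goes to a separate SAP. Protocol 11.3 says: "When follow-up is complete for the primary analysis based on 12-month follow-up, the data base will be locked", and then: "Information post-12 months will remain fully confidential until completion of 18-month follow-up".

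Eye examinations do not stop at Month 12. Protocol 10.2.3 schedules them monthly from Month 13 to Month 17 and again at Month 18. Under Protocol 10.2, Months 13 to 17 cover the study eye only.

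**The concern.** A rule that takes the later of Month 12 and the last visit has no upper limit. The lock comes when 12-month follow-up is complete, so subjects enrolled earlier will usually have visits beyond Month 12 by then. A programmer who follows 8.5 as written would put those visits into the 12-month tables; one who follows SAP 1 would not. The plan does not say which governs.

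Two things are at stake. The first is release, by arm, of information that the protocol keeps confidential until 18-month follow-up is complete. The second, in the single-endpoint tables only, is that arms with more early-enrolled subjects would be read later than the others. The 4 mg arm exists only in Part 2, so it would have the shortest follow-up. Findings that accumulate, such as lens changes, could then differ between arms with no true difference.

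**Working it through.** **1. The time limits side by side**

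| Output | Upper limit stated |
|---|---|
| SAP 8.2, adverse events | First year, ending before the Month 12 injection; fallback if there is none |
| SAP 8.4, vital signs by visit | Month 12 visit |
| SAP 8.4, change to the last measurement | None |
| SAP 8.6, laboratory values by visit | Month 12 visit |
| SAP 8.6, notable laboratory values | Month 12 before treatment; fallback if there is no Month 12 visit |
| SAP 8.6, change to the last value observed | None |
| SAP 8.5, both lists | Later of Month 12 and last visit |

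SAP 8.5 is the only place that names Month 12 and then, without condition, prefers anything later.

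**2. What the rule does, by type of subject**

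- Month 12 and a later visit in the data: the later visit is used.
- Last visit is Month 12: Month 12 is used, as intended.
- Withdrawn with a last visit at, say, Month 9: the later of the two is a Month 12 examination that does not exist. SAP 3.4.2 treats it as missing and SAP 8 does not impute safety data. The sensible outcome, Month 9, is not what the words say.

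This pattern suggests a drafting slip for Month 12 or, if missing, the last earlier visit.

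**3. Share of each arm from Part 1**

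Arm sizes are from Protocol 11.3 and agree with the allocation: 77/3 = 25.7 (stated as 26), and 200 in 1:2:2 = 40/80/80.

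- 2 mg: 26/(26 + 40) = 26/66 = 39.4%
- Sham: 26/(26 + 80) = 26/106 = 24.5%
- 4 mg: 0/80 = 0%

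Part 1 recruitment was complete at Amendment C (Protocol 6). Protocol 9.1.2 also provides for long follow-up: "Subjects in Part 1 who have received greater than or equal to 18 months of Study Drug treatment will be discontinued".

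**4. Mean last-visit month by arm**

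Assumptions: every Part 1 subject has reached Month 18 at the lock, Part 2 has mean last visit *m*, there is no dropout, and the Sham column pools both Parts. The mean is (n1 × 18 + n2 × m)/(n1 + n2), where n1 and n2 are the arm's Part 1 and Part 2 numbers.

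| m | 4 mg | Sham | 2 mg |
|---|---|---|---|
| 12 | 12.0 | 13.5 | 14.4 |
| 15 | 15.0 | 15.7 | 16.2 |
| 16.5 | 16.5 | 16.9 | 17.1 |

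Under these assumptions the arms agree only if m = 18. That cannot hold at a lock taken when the last Part 2 subject reaches Month 12.

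**5. Illustrative size in the single-endpoint tables**

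Further assumptions: 2% per month turn abnormal in every arm, findings persist, and all Part 2 subjects are read at month m. The risk by month t is 1 - 0.98^t:

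- t = 12: 0.2153
- t = 15: 0.2614
- t = 16.5: 0.2835
- t = 18: 0.3049

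The 4 mg minus Sham gap is -(26/106) × (risk at 18 - risk at m):

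- m = 12: -0.2453 × (0.3049 - 0.2153) = -2.2 points (4 mg 21.5%, Sham 23.7%; 2 mg 25.1% with weight 26/66)
- m = 15: -0.2453 × (0.3049 - 0.2614) = -1.1 points
- m = 16.5: -0.2453 × (0.3049 - 0.2835) = -0.5 points

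With m = 12 and the monthly rate varied from 1% to 3%, the gap runs from -1.3 to -2.8 points.

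**6. Monthly tables**

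Each monthly table compares arms at the same visit. Longer Part 1 follow-up adds rows for Months 13 to 18 and leaves Months 1 to 12 unchanged. The only problem there is disclosure.

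**The case against.** The best defence is that the governing text already limits the rule. The SAP is confined to one-year data, and the protocol locks the database for the 12-month analysis and protects what follows. If the last available visit means the last one in the one-year data, completers contribute Month 12 and withdrawers their last visit. That is a fair account of the likely intent, and a data cut at Month 12 would prevent the leak. But it works only by making the word later inoperative, and the plan does not state the cut in 8.5.

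The SAP also uses a later-of rule in 8.2 and 8.6. There it applies only when the Month 12 injection or visit is missing, so a late examination can legitimately fall in the first year. This shows that the construction has a proper use; 8.5 omits the condition.

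A reader might infer that 4 mg will look safer than it is, by about two points. The documents do not support that. They do not give follow-up at the lock, and -2.2 points puts every Part 2 subject at exactly Month 12, although early Part 2 enrollees will be further on. The model also treats findings as irreversible, whereas a shift table shows status at one visit, and Protocol 4.3 reports post-injection conjunctival and corneal findings that had cleared by the next injection. Accumulation is plausible for lens status but is not shown for the whole list.

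The practical weight is also limited. The tables are descriptive, and ocular adverse events, the main safety output, are restricted to the first year.

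**Conclusion.** The wording of SAP 8.5 is wrong as it stands. It conflicts with SAP 1 and Protocol 11.3 and departs from the explicit limits in 8.2, in 8.4 by visit, and in 8.6 by visit and for notable values. That conclusion rests on the text alone.

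Unequal follow-up by arm is a possible further effect, confined to the single-endpoint tables. Its direction follows from the Part 1 shares if Part 1 has the longer follow-up. Its size is illustrative: about -2.2, -1.1 or -0.5 points for 4 mg minus Sham as Part 2 follow-up goes from 12 to 15 to 16.5 months, given 2% per month, persistent findings, Part 1 at Month 18 and no dropout. A smaller side effect is that study and fellow eyes could be read at different times, because Months 13 to 17 examine the study eye only.

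Nor do the documents show that confidential data will in fact be released; that depends on how the data cut is made. The primary analysis, the efficacy tests and alpha are not affected. This should be corrected before the 12-month lock, but it is a safety-table matter and not a threat to the trial's main conclusion.

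**What to change.** Change the SAP wording in three places.

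- **8.5, first list:** use the Month 12 pre-injection examination, applying the Section 3.4.2 visit windows, or, if it is missing, the last examination within the first year as defined in Section 8.2.
- **8.5, second list:** tabulate shifts from Baseline at each monthly visit through the Month 12 pre-injection examination, and limit the pre- to post-injection tables to injections before Month 12.
- **8.4 and 8.6:** apply the same first-year cut to the change to the last measurement and the change to the last value observed.

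One detail needs care when borrowing the 8.2 definition. If there is no Month 12 injection, it can run to 30 days after the last injection. For a subject who misses Month 12 and resumes later, that would again pass Month 12, so the SAP should say that the last injection means the last one before Month 12.

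The cost is SAP text and the matching table programming. No new data are needed, and the post-Month-12 examinations remain available for the separate 18-month SAP.

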### 4.3 Clinical Data

In a phase 1 study, which enrolled patients diagnosed with geographic atrophy, subjects received treatment with three initial intravitreal injections of Zimura™ 0.3 mg/eye or 1 mg/eye, administered at Day 0, Week 4 and Week 8 with a follow up visit at Week 16. Patients received two subsequent injections at Week 24 and Week 36 followed by a final follow up visit at Week 48. [REDACTED]

[REDACTED]

Standard safety assessments were performed for ophthalmic variables which included visual acuity (VA), intraocular pressure (IOP), ophthalmic examination, Fundus Auto-Fluorescence (FAF), Fluorescein Angiography (FA), and Spectral-Domain Optical Coherence Tomography (SD-OCT) together with adverse events (AEs), vital signs, and laboratory variables. [REDACTED]

[REDACTED]

[REDACTED]

[REDACTED] Fifteen patients (32%) had AEs, predominantly Eye Disorder AEs in the study eye (SE), assessed to be related to the injection procedure. The most frequently reported ocular AEs were

conjunctival hemorrhage (4 patients, 9%), corneal edema (4 patients, 9%), and dry eye (3 patients, 6%). No other study eye AEs were reported by more than two patients. The majority of AEs were mild or moderate in severity. There were 2 patients with AEs of severe intensity: gastrointestinal inflammation and nasopharyngitis.

Five patients experienced serious adverse events (SAEs), namely device failure, pelvic fracture, angina pectoris, chest pain, gastrointestinal inflammation, but none were related to the study drug or injection procedure. There were no discontinuations due to AEs.

Vital signs and laboratory assessments did not show any particular clinically significant patterns or changes. Study eye (SE) ophthalmic examinations were mostly normal. There were some transient findings post-injection (conjunctiva/sclera and cornea) which resolved prior to the next injection. Vitreous haze was also reported for a few patients. IOP showed a small mean increase following injections but no indication of any cumulative increase. Visual acuity (VA) assessments did not show any safety concerns.

[REDACTED]

[REDACTED]

[REDACTED]

[REDACTED]

[REDACTED]

[REDACTED]

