## 8.6 CLINICAL LABORATORY DETERMINATION

- All laboratory data will be listed and values falling outside normal ranges will be identified, whether they will be deemed clinically relevant or not.
- Laboratory data will also be summarized in tables presenting values at each scheduled visit up through the month 12 visit
- Value changes from Baseline to each scheduled visit up through the month 12 visit
- A summary table of all analytes with the Baseline mean and the mean change from Baseline to the last value observed
- A summary table of all analytes with the Baseline median and the median change from Baseline to the last value observed

for the following parameters: hematological parameters (hemoglobin, white blood cells, platelets, neutrophils (absolute numbers), lymphocytes (absolute numbers), monocytes (absolute numbers), eosinophils (absolute numbers), basophils (absolute numbers), renal function parameters (serum creatinine and BUN), hepatic function parameters (serum bilirubin, alkaline phosphatase, GGT, SGOT/AST and SGPT/ALT), electrolytes (sodium, potassium, chloride, bicarbonate, calcium and phosphate), urinalysis parameters (complete urinalysis including specific gravity, protein, blood, etc.).

The incidence of subjects with "Notable Laboratory Values" after the first dose of study drug will be evaluated using the criteria for Notable Laboratory Values given below. Only data collected in the first year after the first dose of study drug, up to the laboratory data taken at the Month 12 visit (before Month 12 treatment is administered) will be included; if there is no Month 12 visit, data will be included up to a target of 365.25 days after date of first dose, or 30 days after the last dose of study drug, whichever is later.

By-subject listings of all notable laboratory values will also be provided; for each subject who has an analyte with a notable value, all values of that particular analyte taken during the study will be presented in the listing, and the notable value, and any values outside of normal limits, will be identified.

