### 8.7 ECG

ECG results will be tabulated at Baseline as "normal", "abnormal, not clinically significant" or "abnormal, clinically significant". At follow-up visits, ECG results will be tabulated as "no change from Baseline", "NOT clinically significant change from Baseline" or "clinically significant change from Baseline". A by-patient listing will be provided for ECGs which are deemed clinically significant.

Continuous data (heart rate; PR, QRS, QT and QTc intervals) will be summarized using mean, standard deviation, median, minimum and maximum values at each scheduled visit, and change from Baseline at each visit.

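### IOP is the only repeated continuous safety variable in SAP section 8 that is summarised without any change, either from Baseline or from the same-day pre-injection reading

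*SAP*

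**What the plan says.** SAP 8.5 plans three IOP outputs. First, "IOP will be summarized by visit, including all pre-injection", after-first-injection and after-second-injection readings. Second, the "percentage of subjects in categories of IOP will be presented by treatment group, visit, and injection time"; no cut-points are given. Third, a plot: "Mean IOP over time of all scheduled measurements". Neither the general conventions (SAP 3.4) nor the opening of SAP section 8 adds a change score.

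The neighbouring sections treat their variables differently:

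- SAP 8.4, vital signs: descriptive statistics "will be used to display the changes from Baseline for pulse and blood pressure (systolic and diastolic"), plus mean change to the last measurement.
- SAP 8.6, laboratory: "Value changes from Baseline to each scheduled visit up through the month 12 visit", plus mean and median change to the last value.
- SAP 8.7, ECG: heart rate and intervals at each scheduled visit "and change from Baseline at each visit".
- SAP 8.5 itself: anterior chamber cells, vitreous haze, vitreous haemorrhage and peripheral retina get shift tables from Baseline and "from pre-injection to post-injection at each monthly injection".

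Protocol 4.3 reports the earlier geographic atrophy study in terms of change: "IOP showed a small mean increase following injections but no indication of any cumulative increase". The rule for giving a second injection (Protocol 7.2) is also partly a change rule, since it refers to a 5 mmHg difference from the same-day pre-injection reading.

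**The concern.** IOP is a named safety endpoint. The two questions the earlier study asked of it, a rise after injection and a rise that accumulates over months, are both about the same eye at two times. The 4 mg arm receives two 100 µL injections at each visit (Protocol 9.1.2), so comparing these rises with Sham matters. A table of absolute values at each time point shows how the average moves. It does not show how many eyes rose or by how much, and an absolute category registers only those rises that cross its cut. Because every other repeated continuous measure in section 8 gets a change summary, this looks like an omission rather than a choice.

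**Working it through.** There is no planned figure to reproduce. The check has a textual part, above, and four short steps. **Inputs from the documents:** 80 subjects per arm for 4 mg v Sham (Protocol 11.3), the second-injection rule (Protocol 7.2), and Baseline as the last value before first dose (SAP 5). **Assumed, because the documents give none:** IOP SD 3 mmHg (range 2.5 to 3.5), equal at both times; within-eye correlation ρ from 0.3 to 0.9; approximately normal readings.

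**1. What the planned table still gives.** With complete pairs, mean(post − pre) = mean(post) − mean(pre). The average rise is therefore recoverable.

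**2. What it does not give.** SD(change) = SD × √(2(1−ρ)), and ρ cannot be obtained from two columns of means and SDs. Take an assumed mean rise of 2 mmHg and SD 3. The share of eyes rising by 5 mmHg or more is 1 − Φ(3 / SD(change)):

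| ρ | SD(change) | share rising ≥ 5 mmHg |
|---|---|---|
| 0.3 | 3.55 | 20% |
| 0.6 | 2.68 | 13% |
| 0.8 | 1.90 | 6% |
| 0.9 | 1.34 | 1% |

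All four rows would produce the same planned means and SDs.

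**3. What an absolute category misses.** Suppose the cut is 21 mmHg (an assumption, since the SAP sets none). An eye going from 11 to 20 is not counted; one going from 20 to 22 is. By simulation with SD 3, ρ = 0.6 and a mean rise of 2, about 13% of eyes rise by 5 mmHg or more. Of those, 85%, 75% and 62% still read 21 or less when the pre-injection mean is 14, 15 and 16 respectively. Nearly all stay below 30.

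One part needs no distributional assumption. Under Protocol 7.2 the reading recorded before a second injection must be at most 21 mmHg or within 5 mmHg of the pre-injection value. A compliant reading above 21 is then a rise of at most 5 mmHg, and a compliant rise of more than 5 mmHg reads 21 or less. At that reading a cut of 21 would pick out eyes that started high and none of the larger rises.

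**4. Precision of an arm difference at one visit.** 95% half-width = 1.96 × SD × √(2/80) × k, where k = 1 for absolute values, √(2(1−ρ)) for change, and √(1−ρ²) when adjusted for the Day 1 value. For SD 3 the absolute half-width is 1.96 × 3 × 0.158 = 0.93 mmHg.

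| ρ | change | Day 1-adjusted |
|---|---|---|
| 0.3 | 1.10 | 0.89 |
| 0.5 | 0.93 | 0.81 |
| 0.6 | 0.83 | 0.74 |
| 0.7 | 0.72 | 0.66 |
| 0.8 | 0.59 | 0.56 |
| 0.9 | 0.42 | 0.41 |

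Over SD 2.5 to 3.5 the absolute half-width is 0.77 to 1.08, and change at ρ = 0.7 gives 0.60 to 0.84. Plain change is less noisy only when ρ exceeds 0.5; adjustment helps at any non-zero ρ.

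**The case against.** The case for leaving SAP 8.5 alone is reasonable, and much of it stands.

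- **Mean rises are visible.** Pre- and post-injection readings at one visit come from essentially the same eyes and are both tabulated and plotted. A reader might infer that an injection-related rise would go unseen. On average it would not.
- **Individual rises are partly covered.** SAP 8.2 counts the preferred term for increased intraocular pressure among ocular TEAEs and tabulates these by eye, relationship and severity. SAP 3.4.1 lists individual data, including tonometry method, and an independent committee reviews safety data (Protocol 12.5). A rise that crosses the cut is counted too: 11 to 25 mmHg is high under a cut of 21.
- **Precision is secondary here.** The IOP summaries are descriptive. A reader might convert the adjusted half-widths into a sample-size gain, 1/(1−ρ²), which is 1.6 at ρ = 0.6 and 2.8 at 0.8. The documents do not support that as a loss in this trial: the correlations are assumed, the SAP plans no inferential IOP comparison, and 8.4, 8.6 and 8.7 do not adjust for Baseline either.
- **Change by visit does not cure dropout.** Safety summaries use observed cases (SAP 8), so an eye that leaves with raised IOP contributes neither a later value nor a later change. Only a change-to-last-measurement summary, as in 8.4 and 8.6, keeps it.
- **Instruments differ.** Goldmann tonometry is required on Day 1 and at Months 6 and 12, but Tono-Pen is allowed at most other visits (Protocol 7.2). Change from Day 1 may then compare two methods, which could lower the correlation.

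None of this supplies the missing distribution of within-eye changes. Adverse event coding depends on a reporting judgement, and a listing is not a summary by arm.

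**Conclusion.** The point holds as a minor improvement. IOP alone among the repeated continuous safety variables in SAP section 8 has no change summary, although the paired readings exist and within-eye rise is the safety question. The loss is confined to the spread of individual changes, rises that stay under an absolute cut, and paired precision. The size of the first two depends on assumed SD, correlation, mean rise and cut-point. The precision gain from plain change is conditional on a correlation above 0.5, which is plausible for same-day readings but not stated. The documents do not support saying that an IOP signal would be hidden altogether, and no primary, secondary or decision-guideline result is affected.

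**What to change.** In SAP 8.5 add, by arm:

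1. Change from Day 1 pre-injection IOP to each later pre-injection IOP and to the last available measurement, as 8.4 and 8.6 already do, so that eyes that leave are counted. Adjust any arm difference for the Day 1 value. Note the tonometry method; Months 6 and 12 give a same-method comparison with Day 1.
2. The paired same-day change from pre-injection to post-injection IOP at each visit, shown separately for the after-first and after-second readings, because the reading before a second injection is recorded only once the Protocol 7.2 condition is met.
3. Categories of these changes beside the absolute categories, with the cut-points for both written down before unmasking.

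The cost is SAP wording and a few extra descriptive columns from data already collected. It needs no new measurement and has no effect on alpha, sample size or trial conduct.
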